#### **5.2.5.1 Take Home Lens Performance Survey**

Each subject will be required to complete four Take Home Lens Performance Surveys. Each enrolled subject will be provided with two surveys at the dispensing of the study lenses. Each subject will complete one survey each week after a minimum of 5 days of wearing the study lenses. Both surveys must be returned to the Investigator at the 2-Week Follow-up Visit and reviewed by the Investigator or designee for completeness. At the 2-Week Follow-up Visit, the subject will be given two additional survey and complete a survey each week after a minimum of 5 days of wearing the study lenses. Both remaining surveys must be returned to the Investigator at the 1-Month Follow-up Visit.

#### **5.2.5.2 Unscheduled Visit**

Additional visits may be scheduled, as necessary, to ensure the safety and well-being of subjects. All additional exams should be fully documented in the subject's record and on Unscheduled Visit e-CRFs, as appropriate. Visits intended to fulfill scheduled visit requirements that fall outside the designated scheduled visit range, are not Unscheduled Visits. In these cases, the visit data will be collected and recorded in the appropriate scheduled visit e-CRF.

If a subject is seen for multiple visits during a given visit timeframe, the data from the visit that is intended to meet the protocol requirements for the scheduled visit should be captured on the visit e-CRF. Where such a determination cannot be made, the first visit within the scheduled visit interval will be used for completion of the protocol required scheduled visit e-CRF. Data from any additional visits within a scheduled visit interval will be captured on an Unscheduled Visit e-CRF.

*NOTE: All VA measurements MUST be made using a phoropter.*

- a. Indicate the reason for the Unscheduled Visit.

*NOTE: If the subject is experiencing problems, complete the entire Unscheduled Visit Form. If this visit is to dispense study materials only and the subject is not experiencing any problems refer to Section 5.2.6.*

- b. Collect the following lens information from the subject:
  - average daily wearing time
  - average hours of comfortable wear
  - total number of days of lens wear
- c. Complete the Symptoms/Complaints section within the Unscheduled Visit Form **using the Rating Scale included in initial shipment.**

- d. If the subject did not come to the visit wearing one or more study lenses, go to step e. Otherwise, evaluate the lenses (while on eye) and record the following assessments:
- distance lens VA
  - over-refraction and distance VA
  - lens wettability
  - lens deposits
  - lens centration
  - lens movement

For each eye, compare the high contrast distance lens VA to the high contrast distance lens VA obtained at the visit at which the lenses were dispensed. If the VA has decreased by 10 letters (0.2 logMAR) or more, explain.

- e. Perform a slit lamp examination (remove the lenses if the subject wore lenses to the visit and place the lenses in a lens case provided filled with *Bausch + Lomb Biotrue™ multi-purpose solution*).

**NOTE:** *All worn, unworn, dispensed, non-dispensed study lenses are to be returned as directed with the materials provided. Worn lenses will be returned DRY in lens cases.*

- h. If the subject will continue to wear their original study lenses the subject MUST re-insert the study lenses (the same pair initially dispensed).
- f. If lenses are replaced at this visit, collect the following information:
- primary reason for replacement
  - dispensed lens sphere power, type, and lot number
  - distance lens VA
  - over-refraction and distance VA
  - lens wettability
  - lens centration
  - lens movement
- g. The following e-CRFs should be completed.
- Unscheduled Visit

If the subject is discontinued or exited at this visit:

- Subject Exit

### **5.2.6 Missed Visits**

If a subject misses the 2-Week Follow-up Visit and cannot be seen prior to the start of the visit range for the next scheduled follow-up visit, the 2-Week Follow-up Visit is considered missed and the subject must be exited from the study.

The Investigator or designee must check the missed visit box on the first page of the applicable e-CRF for that visit.

See Section 3.3.5 Lost to Follow-Up for applicable instructions for subjects who do not return for the final 1-Month Follow-Up Visit.

### **5.2.7 Product Dispensing Only Visit**

If a subject is seen for resupply or replacement of study materials and the subject is not experiencing any problems, a complete exam is not required. If any assessment is performed, then an Unscheduled Visit Form must be completed instead of a Product Dispensing Only Form.

If study lenses are dispensed, collect the following information and record in the Product Dispensing Only e-CRF Form and Product Accountability Log (if applicable):

- visit date
- subject ID number
- subject initials
- primary reason for lens replacement
- dispensed lens sphere power, quantity, type, and lot number

*NOTE: All worn, unworn, dispensed, non-dispensed study lenses are to be returned as directed with the materials provided. Worn lenses will be returned DRY in lens cases.*

### **5.2.8 Post-Study Follow-up Visit**

If a subject requires further follow-up upon discontinuation or completion of the study, the Investigator must schedule post-study follow-up visits, as necessary.

*NOTE: All VA measurements MUST be made using a phoropter.*

- a) Remove any contact lenses the subject may be wearing. Perform a slit lamp examination (remove the lenses if the subject wore lenses to the visit). Record the results in the subject's e-CRF.
- b) Complete an ocular examination without lenses on the eyes, including spherocylindrical refraction and distance BSCVA.
- c) The Investigator is required to follow the subject until the condition no longer warrants further follow-up for study purposes. A Post-Study Follow-up Visit e-CRF must be completed for each of these visits.
- d) The following e-CRFs should be completed and submitted.
  - Post-Study Follow-up Visit

## **5.3 Study Completion**

Bausch + Lomb Clinical Affairs will notify the Investigator when to contact the IRB/EC to inform them that the study is complete.

### **5.3.1 Study Termination/Suspension**

If during the study it becomes evident to the Sponsor that the study should be stopped prematurely or placed on hold, appropriate notification will be given to the Investigator(s) and IRB/ECs, as applicable. Bausch + Lomb Clinical Affairs will instruct the Investigators to stop/restart dispensing study materials and will arrange for study closeout, if applicable, at each site.

#### **5.4 Concomitant Medications/Therapy**

Ocular medications or systemic or topical medications that, in the Investigator's opinion, could potentially affect ocular physiology or lens performance are also prohibited, unless medically necessary during the course of the study. If used during the course of the study, these medications must be recorded in the source document and the appropriate e-CRF.

#### **5.5 Protocol Deviations**

The date of and reason for deviations will be documented in all cases. Significant or major protocol deviations impacting the safety of the subject or the integrity of the study must be reported by the Investigator to the IRB/EC, CRO and Sponsor, B+L Clinical Affairs immediately. Reporting of all other protocol deviations must adhere to the requirements of the governing IRB/EC.

Subjects may continue to participate until the end of the study, unless the protocol deviations put the subject at risk or the subject's condition requires that they be discontinued from the study.

### **6.1 ADVERSE EVENTS**

#### **6.2 Adverse Events**

Throughout the course of this study, all efforts will be made to remain alert to possible Adverse Events (AEs). The term "AEs" includes both Serious Adverse Events (SAEs) and Significant Non-Serious Adverse Events. Each is defined below.

If an AE occurs, the first concern will be the safety of the subject and appropriate medical intervention will be made. All AEs (serious AEs and significant non-serious AEs) that occur will be reported in this study.

All adverse events occurring after signing of informed consent and through the subject's end of participation in the study must be reported. All adverse events must be followed until the event resolves or stabilizes.

#### **Serious Adverse Events**

Serious adverse events (SAEs) are those events that result in, or have potential to cause, either permanent impairment of an ocular function or damage to an ocular structure, and may necessitate medical or surgical intervention.

Serious adverse events may include any hazardous, **sight-threatening conditions** occurring after exposure to the test article, including the following:

- A presumed infectious ulcer (defined as a progressive erosion of the corneal tissue). For the purposes of reporting, a corneal ulcer which has *any* of the following characteristics should be considered in this category:
  - central or paracentral location;
  - penetration of Bowman's membrane;
  - infiltrate  $\geq 2$  mm diameter;
  - associated with iritis Grade 2 or greater;
  - associated with any increase in intraocular pressure;
  - culture positive for microorganisms;

- increasing size or severity at subsequent visits.

- Note: Signs of a presumed infectious ulcer may include irregular focal infiltrates; active lesions with raised edges; significant diffuse infiltration; anterior corneal to mid-stromal involvement; erosion with overlying staining; conjunctival and lid edema; anterior chamber reaction (iritis); severe bulbar and limbal redness. Symptoms associated with a presumed infectious ulcer (microbial keratitis) may include pain of rapid onset; severe redness; purulent or mucopurulent discharge; tearing; photophobia.
- Any central or paracentral (within 6mm of cornea) corneal event that results in permanent opacification (such as vascularization).
- Any serious adverse ophthalmic events including hypopyon and hyphema.
- Any neovascularization within the central 6 mm of the cornea.
- Permanent loss of two or more lines of BSCVA.
- All cases of iritis.

### **Significant Non-Serious Adverse Events**

Significant Non-Serious Adverse Events should include:

- Peripheral non-progressive non-infectious corneal ulcers;
- All symptomatic corneal infiltrative events;
- All cases of corneal staining greater than or equal to Grade 3;
- A temporary loss of two or more lines of BSCVA (for greater than or equal to 2 weeks);
- Neovascularization cases Grade 2 or greater;
- Any ocular event that necessitates temporary lens discontinuation of greater than or equal to 2 weeks.

### **Adverse Event Treatment and Culturing**

With any AE, treat the subject as appropriate to prevent further complications and to potentially resolve the event consistent with the standard of care.

For purposes of this study, the Sponsor requests that in the case of suspected bacterial conjunctivitis, corneal ulcer, or ocular infection a culture must be obtained. Appropriate cultures must be taken to identify the pathogenic organism following the Investigator's standard culturing techniques (e.g., lid, cul-de-sac, cornea, lens and lens case with customary growth media). Forward the cultures to your local clinical laboratory for analysis and report culture results to the Sponsor.

**Contact Bausch + Lomb Senior Director of Clinical Affairs with questions regarding culturing.**

### **6.3 Medical Treatment (non-Adverse Events)**

In the event that a subject requires medical treatment (prescription medication) for an ocular condition, treat the subject as appropriate to prevent further complications and to potentially resolve the event.

## **Guidelines for Reporting Adverse Events (Serious and Significant Non-Serious) and Medical Treatments (Non AE)**

In the case of an AE (Serious and Significant Non-Serious) or Medical Treatment (non AE), the Investigator must:

- 
- Indicate on the Initial AE/Medical Treatment Notification Form whether the AE/Medical Treatment is presumed to be not study related, lens-related, solution-related or both lens/solution related.
  - Ensure that the subject's identity is protected and the subject's identifiers in the clinical trial are properly mentioned on the form.
  - BEGIN TREATMENT OF THE AE IMMEDIATELY BY A SUITABLY LICENSED EYE CARE PROFESSIONAL.
  - Enter the AE/Medical Treatment into the e-CRF within 3 business days of submitting the Initial AE/Medical Treatment Notification Form.
  - Continue to update the e-CRF, if applicable, each time the subject is seen during the management of the incident and at resolution of the incident. Whenever possible, it is suggested that the Investigator take photographs of all AEs and forward them to the Sponsor.
  - Cases requiring medical treatment will be evaluated by the Sponsor. Upon review of the medical treatment, Bausch + Lomb Clinical Affairs representatives may contact the Investigator to request further information concerning the treatment.
  - Submit all bills, prescription receipts, and culture reports/fees related to the AEs and Medical Treatment to Bausch + Lomb Clinical Affairs. Expenses incurred for study-related medical treatment will be paid by Bausch + Lomb Clinical Affairs.

### **6.3.1 Reporting of Complaints for Ancillary Marketed Bausch + Lomb Products**

For Bausch + Lomb marketed products used as ancillary products in the study, the Investigators should report any complaints, malfunctions or similar events related to these products as they would in their normal clinical practice and in accordance with reference information as outlined on the commercial packaging.

## **7.1 Statistical Methods**

### **7.2 Study Endpoints**

#### Primary Effectiveness Endpoints

- For each question on the take home questionnaire at each of four week-long intervals, the proportion of subjects providing a response in the top 3 boxes.
  - Note that these endpoints are not pass/fail criteria for the study. Rather, these are the most important data that will be evaluated.

#### Secondary Effectiveness Endpoints

- Lens performance survey (100 point scales) questions.

Study ROC2-17-014 - Protocol

- Comfort upon insertion
- Overall comfort
- Comfort at end of day

Secondary Safety Endpoints

- The proportion of subjects with any slit lamp findings grade 2 or greater at any time.

[figure not shown]
Hypotheses

The following hypotheses will be tested for each question in the take home performance questionnaire at each week.

1. The null hypothesis is that the proportion of subjects providing a response in the top three categories is equal between the treatment groups.
2. The alternative hypothesis is that the proportion of subjects providing a response in the top three categories is not equal between the treatment groups.

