#### **3.3.1.2 Exclusion Criteria**

1. Subjects participating in any drug or device clinical investigation within two weeks prior to entry into this study and/or during the period of study participation
2. Subjects who are women of childbearing potential (those who are not surgically sterilized or postmenopausal) are excluded from participation in the investigation if they meet any one of the following conditions:
  - she is currently pregnant
  - she plans to become pregnant during the study
  - she is breastfeeding

3. Subjects with any systemic disease currently affecting ocular health or which in the Investigator's opinion may have an effect on ocular health during the course of the study.
4. Subjects using any systemic or topical medications that will, in the Investigator's opinion, affect ocular physiology or lens performance.
5. Subjects with an active ocular disease or who are using any ocular medication.
6. Subjects who are not correctable to 32 letters (0.3 logMAR) in each eye with soft spherical contact lenses.
7. Subjects who currently wear monovision or multifocal contact lenses.
8. Subjects with refractive astigmatism of 0.75 D or greater in either eye.
9. Subjects who are current Acuvue Oasys wearers who have previously been unsuccessful in wearing Acuvue Vita and/or Ultra contact lenses.
10. Subjects with anisometropia (spherical equivalent) of greater than 2.00 D.
11. Subjects with any grade 2 or greater finding during the slit lamp examination (refer to Appendix B for methods of clinical evaluation). Subjects with corneal infiltrates, of ANY GRADE, are not eligible.
12. Subjects with any "Present" finding during the slit lamp examination (refer to Appendix B for methods of clinical evaluation) that, in the Investigator's judgment, interferes with contact lens wear.
13. Subjects with any scar or neovascularization within the central 6 mm of the cornea. Subjects with minor peripheral corneal scarring (that does not extend into the central area), that in the Investigator's judgment, does not interfere with contact lens wear, are eligible for this study.
14. Subjects who are aphakic.
15. Subjects who are amblyopic.
16. Subjects who have had any corneal surgery (e.g., refractive surgery).
17. Subjects who meet any of the following criteria:
  - the subject is an employee of the investigative site
  - the subject, or a member of the subject's household, is an employee of a marketing research firm

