#### **4.8 Masking/Unmasking**

Both the Investigator and the subjects will be masked to the study treatment. An unmasked designee at each site will be responsible for dispensing study products to the subjects according to the randomization schedule. The randomization schedule will be produced by the Sponsor statistician not otherwise involved in the study until after the database is locked.

Randomization will be completed by the unmasked designee by providing each subject's treatment assignment after the subject has been assigned a subject number (i.e., randomized). The subjects will be assigned randomization numbers sequentially as they are enrolled. The unmasked designee will open the blister packs by removing the foil out of the subject's sight (subject MUST insert lenses). The unmasked designee is also responsible for maintaining study lens inventory, randomization schedule and the Product Accountability Log in a masked fashion.

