**7.3 Sample Size**

The sample size will be 130 subjects per group, which is the maximum affordable sample size. This sample size will have a varying ability to detect differences between the groups depending on the proportions. For example, a two-group  $\chi^2$  test with a 0.050 two-sided significance level will have 80% power to detect the difference between a Smaller proportion,  $\pi_1$ , of 0.500 and a Larger proportion,  $\pi_2$ , of 0.670 when the sample size in each group is 130. Additional cases, assuming the same significance level, power, and sample size are shown in the following figure.

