#### 7.5 Study Populations

Subject eyes will be included in all summaries under the treatment that they actually received. Analyses of safety data will include all dispensed subjects. All other summaries will include all eligible, dispensed subjects.

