#### 7.6 Statistical Analysis

Primary and secondary analyses will be performed on all eligible, dispensed eyes (completed and discontinued eyes pooled) for efficacy endpoints and for all dispensed eyes (completed and discontinued eyes pooled) for safety endpoints.

Questionnaire responses to the take home questionnaire will be summarized using categorical summary statistics by treatment and week. The proportion of subjects providing a response in the top three categories will be compared between treatments using chi-square tests by week. A Fisher's exact test will be used instead of a chi-square test when any cell in the contingency table has an expected count less than five.

Comfort related lens performance survey question results will be summarized using continuous summary statistics by treatment group and visit. Two-sided two-sample t-tests will be used to compare the treatment groups by visit.

The proportion of subjects with any slit lamp findings grade 2 or greater will be summarized categorically by treatment group and visit. Two-sided Fisher's exact tests will be used to compare the groups by visit.

Missing data will not be imputed.

There will be no adjustments for multiple comparisons.

There are no planned interim analyses.

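### The slit lamp safety comparison ignores the Screening grade: on seven of the eight graded scales a subject may enter at grade 1 and becomes an event on a one-grade rise

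*Combined protocol and SAP*

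**What the plan says.** Section 3.3.1.2, exclusion 11, bars "Subjects with any grade 2 or greater finding during the slit lamp examination" and adds: "Subjects with corneal infiltrates, of ANY GRADE, are not eligible". An eligible subject may therefore start at grade 0 or 1 on seven of the eight scales that Appendix B grades from 0 to 4 (epithelial edema, microcysts, corneal staining, limbal injection, bulbar injection, tarsal abnormalities, neovascularization), and only at grade 0 for infiltrates.

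Section 7.2 lists one safety endpoint: "The proportion of subjects with any slit lamp findings grade 2 or greater at any time". Section 7.6 then says: "The proportion of subjects with any slit lamp findings grade 2 or greater will be summarized categorically by treatment group and visit", and "Two-sided Fisher's exact tests will be used to compare the groups by visit". Section 7.5 sets the population: "Analyses of safety data will include all dispensed subjects". On masking, section 4.8 says: "Both the Investigator and the subjects will be masked to the study treatment".

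Slit lamp results are entered in the e-CRF at Screening (section 5.2.1). In the text available, sections 7.2, 7.5 and 7.6 and Appendix B contain no analysis that uses the Screening grade, no shift table, no confirmatory reading and no check of agreement between graders.

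**The concern.** The event threshold sits one step above the highest grade allowed at entry on seven scales, and that step is partly a matter of judgment. In Appendix B, grade 1 and grade 2 edema differ in how discernible the haze is. The two injection scales separate these grades by how slight the redness is and by whether it occupies one quadrant or more. One such reading, on any scale and in either eye, makes the subject an event at that visit.

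Subjects who enter at grade 1 are closer to the threshold than those who enter clear, yet the analysis treats them alike. If some grade 1 eyes are read as grade 2 without real change, both groups gain events unrelated to the lens. A finding of no difference would then say less about safety than it seems to. The table would also not show whether an event was a new finding in a clear eye or a one-grade move.

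**Working it through.** **1. The plan's own figure.** Section 7.3 gives 80% power for 0.500 against 0.670 with 130 per group at two-sided 0.05. For the chi-square test, power = Φ{[Δ√n − 1.96√(2p̄(1−p̄))] / √(p₁(1−p₁)+p₂(1−p₂))}. With Δ = 0.17, n = 130 and p̄ = 0.585 this is Φ{[1.938 − 1.366]/0.686} = Φ(0.834) = 79.8%. It reproduces. No such figure is given for the safety endpoint.

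**2. Number of exposed readings.** 7 scales × 2 eyes = 14 per visit, or 28 over the 2-Week and 1-Month visits. Section 7.6 tests by visit, so 14 is the relevant count.

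**3. Share of false events (assumed inputs).** Let g be the share of subjects truly at grade 1 on a given scale (both eyes) and r the chance that a grade 1 eye is read as 2. A grade 0 eye is never read as 2. Admission requires no grade 2 reading at Screening. With m = 2 if reading errors are independent between eyes and m = 1 if they are fully shared, the share of admitted subjects with a false event at one visit is

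1 − {[(1−g) + g(1−r)^(2m)] / [(1−g) + g(1−r)^m]}^7.

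- Middle setting (g = 10%, r = 5%), independent eyes: 1 − (0.98145/0.99025)^7 = 6.1%.
- Middle setting, shared errors: 1 − (0.99025/0.99500)^7 = 3.3%.
- Lowest setting (g = 5%, r = 2%, shared): 1 − (0.99802/0.99900)^7 = 0.7%.
- Highest setting (g = 20%, r = 10%, independent): 1 − (0.93122/0.96200)^7 = 20.4%.

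Over two visits the numerator exponent becomes 3m. The middle setting is then 11.3% or 6.3%, and the range is 1.4% to 34.1%. Per-visit noise is thus about half the two-visit noise.

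Screening does not add to this. Without the admission rule, the middle setting with independent eyes gives 1 − 0.99025^7 = 6.6% per visit, against 6.1% with it.

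**4. Effect on the comparison (assumed true rates).** If p is the true event rate and q the noise, the observed rate is 1 − (1−p)(1−q). For 5% against 15% with q = 5%, the observed rates are 1 − 0.95×0.95 = 9.75% and 1 − 0.85×0.95 = 19.25%. The difference shrinks only from 10 to 9.5 points, but the ratio falls from 3.0 to 1.97. Most of the power loss comes from the higher background rate. Power of the two-sided Fisher test at 130 per group, by full enumeration:

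| True rates | q = 0 | q = 5% | q = 10% |
|---|---|---|---|
| 1% vs 9% | 82% | 47% | 32% |
| 2% vs 10% | 72% | 44% | 30% |
| 5% vs 15% | 72% | 53% | 40% |
| 10% vs 22% | 71% | 58% | 48% |

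Small noise costs little: 5% vs 15% at q = 1% still has 68%.

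**5. Validity.** With a true rate of 5% in both arms, the Fisher type I error runs from 2.2% to 3.7% as q goes from 0 to 30%. Equal noise does not produce a false difference.

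**6. What stratification recovers.** In simulation at 130 per group, an exact test stratified by any grade 1 finding at Screening gained about 2 to 16 points of power over the unstratified Fisher test. For example, at 1% vs 9% with 6 points of noise and half the subjects at grade 1 (so 12% noise in that half and none in the other), power rose from 42% to 47%. Stratification returns part of the loss, not all of it.

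**The case against.** The strongest reply is that matching the event threshold to the entry cut-off is deliberate and sensible. Since nobody eligible enters at grade 2, every event in an eligible subject is already a recorded rise of at least one grade after entry. When dispensing falls on a separate day, section 5.2.2 repeats the examination and reconfirms eligibility. Graders are masked, several grade boundaries have discrete anchors (a quadrant count, a microcyst count), the endpoint is secondary with no stated hypothesis or power claim, and section 6.2 captures serious and significant events separately. All of this stands. It limits the consequence, but one grade is the smallest step on the scale and the analysis still leaves out a recorded baseline value.

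A reader might infer that noise does create events here and does hide a lens difference. The documents do not support that. They give no grade 1 prevalence, expected event rate or repeatability, and the assumed range runs from negligible to severe.

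A reader might also conclude that the endpoint should require a two-grade rise. That would discard every true change from 1 to 2. At 5% vs 15%, a rule that removed all noise but kept 60% of true events would have 43% power, and at 50% kept 34%, against 40% for the present rule with 10 points of noise. Section 6.2 also lists neovascularization at grade 2 as a significant event, so the protocol itself gives weight to that grade.

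**Conclusion.** The endpoint is sound and the Fisher tests are valid. What is missing is any use of the Screening grade in comparing the groups or describing the events. The dilution is conditional: it matters only if grade 1 at entry is common and is read as grade 2 often enough. Under the middle assumptions (10% at grade 1 per scale, 5% misreading), noise is 3.3% to 6.1% of subjects per visit. Noise of 5 points would cost between 13 points of power (71% to 58%, at 10% vs 22%) and 35 (82% to 47%, at 1% vs 9%). These figures also assume upward-only errors that are independent between visits and equal in the two arms. Masking makes the last of these plausible. This is a free improvement to the analysis and not the correction of an error.

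**What to change.** Keep the endpoint at grade 2 or above and change section 7.6 in two ways, before unmasking.

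1. Compare the groups at each visit with an exact conditional test stratified by whether the subject had any grade 1 finding at Screening. State which examination counts when dispensing is on a separate day. State also that a subject dispensed in error at grade 2 or above falls in the stratum with findings, since the safety set is all dispensed subjects. If no subject has a grade 1 finding, the test reduces to the planned Fisher test.
2. Add a shift table from Screening grade to worst post-dispensing grade, by group and scale.

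The cost is a few sentences and one table. The Screening grades are already in the e-CRF, no visit or measurement is added, and no true event is dropped. The gain in power is modest and depends on the assumptions above. The shift table is useful whatever the noise turns out to be, because it shows how many events started from grade 1.
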